10.4.3 Standard Digital ECG

Treatment Cohort Period 1

For the ECG measurements, a summary of raw values and change from previous study baseline will be provided at each scheduled time point in the Cumulative Study Period based on the Safety Set for the following standard digital ECG measurements: PR, QT, and QT corrected for HR (QTc) intervals (Fridericia's correction [$QTcF = QT/RR^{1/3}$]), QRS duration, and HR. In addition, the mean QTcF values will be plotted against visits in the Cumulative Study Period.

The number and percentage of subjects meeting at least one threshold analysis criterion during the treatment-emergent period will be summarized following the presentation format in Section 10.1.2. The threshold analysis criteria are provided in Appendix H. The number and percentage of subjects with heart rate (bpm) < 40, < 50 and >90 will be summarized. A listing containing individual subject ECG measurements including all parameters and assessments at all visits will be provided. A separate listing of subjects meeting at least 1 threshold analysis criterion during the treatment-emergent period will also be presented.

The number and percentage of subjects with shift changes from baseline, based on the worst on-treatment overall ECG evaluation, will be tabulated.

10.4.4 Vital Signs

Treatment Cohort Period 1

For the vital signs measurements, the raw values and change from previous study baseline values will be summarized at each scheduled time point in the Cumulative Study Period based on the Safety Set: systolic and diastolic blood pressure (mm Hg), body temperature (°C), HR (beats per minute), respiratory rate (breaths per minute), weight (kg), height(m) and BMI (kg/m²).

The number and percentage of subjects meeting at least 1 threshold analysis criterion during the treatment-emergent period will be provided following the presentation format in Section 10.1.2. The threshold criteria are provided in Appendix H. A listing containing individual subject vital signs measurements including all parameters and assessments at all visits will be provided.

In addition, number and percentage of subjects for the following categories during the treatment-emergent period will be summarized.

Table 10-7 Additional Vital Signs Categorical Analyses

Meeting criteria	SBP (mmHg)	DBP (mmHg)	Heart rate (bpm)
For at least once	>140	>90	<40
	>140 and >10 increase from baseline	>90 and >5 increase from baseline	<50
	>140 and >20 increase from baseline	>90 and >10 increase from baseline	>90
	>10 increase from baseline	>5 increase from baseline	
	>20 increase from baseline	>10 increase from baseline	
For at least twice	>120	>80	
	>140	>90	
	>120	>80	

Number and percentage of subjects with SBP >120 mmHg at each visit and those with DBP > 80 mmHg at each visit in the Cumulative Study Period will be provided.

Potentially abnormal SBP and DBP by their percentiles adjusted for sex, age and height will be provided, including

- Number and percentage of subjects with categories $\geq 90\%$ -<95%, $\geq 95\%$ -<99% + 5 mmHg and $\geq 99\%$ + 5 mmHg)
- Number and percentage of subjects with SBP and DBP percentiles $\geq 95\%$ once and twice during the treatment-emergent period will be provided.
- Number and percentage of subjects with SBP and DBP percentiles $\geq 95\%$ at each visit will also be provided.

The height adjustment will be based on height-for-age-z-scores and their corresponding percentiles using the standard normal distribution. The height percentiles will be further mapped per the following rules:

Table 10-8 Grouped Percentiles for Height-for-age Z-scores

Calculated Percentiles (%)	Grouped Percentiles (%)
0 – <7.5	5
7.5 – <17.5	10
17.5 – <37.5	25
37.5 – <62.5	50
62.5 – <82.5	75
82.5 – <92.5	90
92.5 – 100	95

The sex and age-adjusted normal range for SBP and DBP for each grouped height percentiles is based on the SBP/DBP table in Appendix K per the National Heart, Lung, and Blood Institute (NHLBI) website (<http://www.nhlbi.nih.gov/health-pro/guidelines/current/hypertension-pediatric-jnc-4/blood-pressure-tables>). A listing of subjects with potentially abnormal SBP or DBP will be provided.

10.4.5 Pulse Oximetry

Treatment Cohort Period 1

The raw values and change from previous study baseline in percent of oxygen saturation measurements at each scheduled time point during the Cumulative Study Period will be summarized with two treatment groups: L200/I-L/I and P-L/I based on the Safety Set. In addition, the mean value at each visit will be plotted for the percent of oxygen saturation.

The number and percentage of subjects with shift changes from previous study baseline (normal/missing and low according to the reference range) to the lowest percent of oxygen saturation during the treatment-emergent period will be tabulated following the safety presentation format in Section 10.1.2.

10.4.6 Ophthalmological Examinations

Treatment Cohort Period 1

For the analysis of slit lamp lens, the number and percentage of subjects with shift changes from previous study baseline (normal versus abnormal) will be tabulated for the Previous Study Period based on the Safety Set, Current Study Period based on 110 Safety Set, and Cumulative Study Period based on the Safety Set at each scheduled time point following the safety presentation format in Section 10.1.2. Ophthalmological examination findings will also be presented as a data listing.

Treatment Cohort Period 2

Ophthalmological examination findings in Treatment Cohort Period 2 will be presented as a data listing.

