12.3 Analysis Periods

Three different dosing periods will be used:

Current Dosing Period refers to the period starting with the initial dose of study drug in Study 110 to the last dose of study drug in Study 110.

Cumulative Dosing Period refers to the period starting with the initial dose of study drug in the previous study to the last dose of study drug in Study 110.

Active Dosing Period refers to the period starting with the initial dose of active treatment to the last dose of active treatment in Study 110.

Within each of the above dosing periods, safety analysis will be based on the treatment-emergent period, which starts from the start of the dosing period to 28 days (inclusive) after the last dose of the dosing period.

Handling of the data during the gap between the previous study and the rollover study will be detailed in the SAP.

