12.4 Statistical Analysis

12.4.1 General Considerations

For the Observational Cohort, summaries will only be provided for the disposition, demographic and baseline characteristics, and SAEs. Summaries will be provided based on all enrolled subjects in that cohort.

For the Treatment Cohort, analyses will be repeated for current dosing period, cumulative dosing period (efficacy only), and active dosing period as shown in Table 12-3. All analyses will be provided using all data, regardless of whether the subjects turn 12 years of age and subsequently switch to LUM 400 mg q12h/IVA 250 mg q12h, to examine the treatment strategy, which includes the age-based dose regimen switch.

Table 12-3 Analysis of Efficacy and Safety in Different Dosing Periods

Period	Efficacy	Safety
Current Dosing Period	X	X
Cumulative Dosing Period	X	None
Active Dosing Period	X	X

- Efficacy analysis (except those related to pulmonary exacerbations, LCI, [REDACTED]) will be based on the FAS for the current dosing period, and based on the IFAS for the cumulative dosing period and the active dosing period.
 - Pulmonary exacerbation-related analysis for the active dosing period will be based on 109FAS by treatment group. The placebo-controlled period for subjects randomized to the placebo arm will be analyzed separately.
 - LCI related analysis will be based on the LCI Analysis Set for the current dosing period, and based on the Integrated LCI Analysis Set for the cumulative dosing period and the active dosing period.

- Safety analysis will be based on the Safety Set for the current dosing period, and based on the Integrated Safety Set for the active dosing period.

All subject data listings for the Treatment Cohort will be referenced using the Integrated All Subjects Set, unless otherwise specified.

Continuous variables will be summarized using the following descriptive summary statistics: the number of subjects (n), mean, standard deviation (SD), median, minimum value, and maximum value.

Categorical variables will be summarized using counts and percentages.

Baseline: The baseline value of each dosing period is defined as the most recent measurement before intake of the first dose of the corresponding dosing period, except if specified otherwise.

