10.1.2.2 Continuous Variable

Treatment Cohort Period 1

For continuous variables, the raw values and change from previous study baseline will be summarized by treatment group (L200/I-L/I and P-L/I) based on Safety Set at each scheduled time point in the Cumulative Study Period. The presentation format is similar as the continuous efficacy variable summary in Table 10-2.

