10.4.8 Spirometry

Treatment Cohort Period 1

Analysis of Predose Spirometry at Each Postdose Visit

Spirometry data will be summarized descriptively as safety-supporting data at each visit during the Cumulative Study Period by treatment group (L200/I-L/I and P-L/I) based on the Safety Set. The following summary (number and percentage of subjects) will be provided:

- Absolute change from previous study baseline in predose ppFEV₁ ≤ -5 percentage points
- Absolute change from previous study baseline in predose ppFEV₁ ≤ -10 percentage points
- Relative change from previous study baseline in predose ppFEV₁ ≤ -5 %
- Relative change from previous study baseline in predose ppFEV₁ ≤ -10 %
- Absolute change from previous study baseline in predose FEV₁ ≤ -0.05L
- Absolute change from previous study baseline in predose FEV₁ ≤ -0.10L
- Relative change from previous study baseline in predose FEV₁ ≤ -5%
- Relative change from previous study baseline in predose FEV₁ ≤ -10%

Subjects with ≥5 percentage points decrease in absolute change from previous study baseline in ppFEV₁ or ≥0.05 L decrease in absolute change from previous study baseline in FEV₁ at any visit during the Cumulative Study Period will be listed based on the Safety Set. The listing will include raw values and absolute/relative changes from previous study baseline in ppFEV₁ and FEV₁ at all visits during the Cumulative Study Period.

Analysis of Serial Spirometry

Based on the 110 Safety Set for the Current Study Period, raw values and absolute change from predose assessment in postdose ppFEV₁ and FEV₁ will be summarized by visit and by time point. The number and percentage of subjects with ≥5, ≥10, ≥15, and ≥20 percentage points decrease in the absolute change from predose to postdose in ppFEV₁ will also be summarized by visit and time point.

The summary tables will include two treatment groups (L200/I-L/I and P-L/I). For treatment L200/I-L/I, separate summaries will also be provided by previous studies (Study 109 and 011B). For both of the summaries, the mean values along with the 95% CIs based on Normal approximation will be plotted against visits and time points.

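### For children who took placebo in Study 109, the SAP measures lens shifts, SpO2 shifts and predose FEV1 falls from a baseline set about 24 placebo weeks before their first LUM/IVA dose

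*SAP*

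**What the plan says.** **Protocol.** Under 12.4.1, baseline for a dosing period is the latest measurement before that period's first dose, unless specified otherwise. The same section says "analyses will be repeated for current dosing period, cumulative dosing period (efficacy only), and active dosing period", and Table 12-3 assigns no safety analysis to the cumulative period. Under 12.3 the active dosing period "refers to the period starting with the initial dose of active treatment to the last dose of active treatment in Study 110". For P-L/I children the current and active periods therefore share one baseline: the last value before the first Study 110 dose. The exceptions listed in 12.4.1 concern LCI, ECG and sweat chloride. Sections 12.4.4.5 to 12.4.4.7 (SpO2, eye examinations, spirometry) name no other baseline.

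**SAP.** Section 10.1 repeats the per-period rule, again allowing exceptions. Later sections then override it:

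- 10.4.6, slit lamp: "shift changes from previous study baseline (normal versus abnormal) will be tabulated for the Previous Study Period based on the Safety Set, Current Study Period" and the Cumulative Study Period.
- 10.4.5, SpO2: "shift changes from previous study baseline (normal/missing and low according to the reference range) to the lowest percent of oxygen saturation" in the treatment-emergent period.
- 10.4.8, predose spirometry: "Spirometry data will be summarized descriptively as safety-supporting data at each visit during the Cumulative Study Period by treatment group". All eight fall criteria use the previous-study baseline, for example "Absolute change from previous study baseline in predose FEV₁ ≤ -0.05L". Children who meet the ppFEV1 or litre trigger "at any visit during the Cumulative Study Period will be listed based on the Safety Set".
- 10.1.2.2, continuous safety variables: "the raw values and change from previous study baseline will be summarized by treatment group (L200/I-L/I and P-L/I) based on Safety Set".

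The lens and SpO2 shift tables follow the format of SAP 10.1.2. P-L/I shifts in Study 110 therefore also feed the 110 Overall column and the pooled L/I Overall column.

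**The concern.** Safety is the primary endpoint, and P-L/I is the only group whose first LUM/IVA exposure falls inside Study 110. The natural question for these children is what changed after they started the drug. A reference value from the start of Study 109 answers a different question: what changed since before 24 weeks of placebo. The answers can differ in either direction, because a count may include change that happened on placebo or miss change that happened on drug.

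The lens result shows why this matters. Protocol 8.2.3 judges the animal lens finding unlikely to be relevant to humans and sees no association in the data so far. It also says an association is not fully excluded, and the eye examinations are there to settle that. A shift table for this purpose should separate placebo-era from on-drug change.

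**Working it through.** **The plan's own figures.** The only precision figures are the intervals in protocol Table 12-1. They reproduce as p ± 1.96·√(p(1−p)/256); for p = 0.1 this gives 0.063 to 0.137. Nothing below depends on them.

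**Step 1. Which value is the reference?**

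| Group | Protocol, current period | Protocol, active period | SAP 10.4.5, 10.4.6, 10.4.8 |
|---|---|---|---|
| P-L/I | before first Study 110 dose | before first Study 110 dose | before first placebo dose in Study 109 |
| L200/I-L/I | before first Study 110 dose | before first dose in Study 109/011B | before first dose in Study 109/011B |

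For P-L/I the SAP matches neither protocol baseline. For L200/I-L/I it matches the active-period baseline, so only their Study 110 column departs from the protocol. There, a shift that arose in the earlier study and persists can be counted again.

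**Step 2. What enters the shift columns?** Under SAP 9.1.2 the Current Study Period window opens at the first Study 110 dose, so every counted observation is on or after that dose. Two patterns are misread for P-L/I:

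- Normal at Study 109 baseline, abnormal by the end of placebo, still abnormal on drug: the SAP counts a shift; the protocol baseline does not.
- Abnormal at Study 109 baseline, normal at Study 110 Day 1, abnormal again on drug: the SAP counts no new shift; the protocol baseline does.

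For the first pattern, let q be the proportion acquiring a persistent abnormality on placebo, and r the proportion of the rest acquiring one on drug. The SAP counts q + (1−q)r and the protocol baseline counts (1−q)r, so the excess is q. The documents give no value for q. Each such child adds 1/256 = 0.4 percentage points to 110 Overall if all 256 enrol. In the 110 P-L/I column each adds 1.0 point for an assumed 100 children (1:1 allocation in Study 109) or 1.5 points for an assumed 67 (2:1). The allocation ratio is not stated.

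**Step 3. Share of the change interval spent on placebo.** Study 109 placebo lasted 24 weeks (protocol 8.2.1). With no roll-over gap, the share at Study 110 week w is 24/(24+w):

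- Day 15: 24/26 = 92%
- Week 24: 24/48 = 50%
- Week 48: 24/72 = 33%
- Week 96: 24/120 = 20%

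These are shares of time, not of events. Scheduled on-drug eye examinations in Study 110 are at Weeks 48 and 96 (or early termination or follow-up), so the last two shares are the relevant ones for the lens.

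**Step 4. Growth and the litre criteria.** SAP Appendix F gives predicted FEV1 = exp(α + β·ln height). For a white boy aged 9, α = −0.063 and β = 2.197. Assumed: height 1.32 m, growth of 2 to 3 cm over the 24 weeks, age row held fixed, constant ppFEV1 of 100% before Day 1.

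- At 1.32 m: 1.728 L
- At 1.34 m: 1.786 L, a gain of 0.058 L (3.4%)
- At 1.35 m: 1.815 L, a gain of 0.087 L (5.1%)

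At the first Study 110 visits, ignoring growth after Day 1, he must lose 0.05 + 0.058 = 0.108 L to 0.05 + 0.087 = 0.137 L since starting drug to be counted as a 0.05 L fall. For the 5% relative fall in litres he must lose 1 − 0.95/1.034 = 8.1% to 1 − 0.95/1.051 = 9.6%. From the Study 110 baseline, two weeks of growth at these rates offset less than 0.01 L. The ppFEV1 criteria are adjusted for height, so this offset does not apply to them. There the difference depends on placebo-period drift and variability, which the documents do not give.

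**The case against.** Much of the opposing case stands.

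- **Both documents permit another baseline.** Each allows exceptions, and the protocol leaves detail to the SAP. SAP Section 3 is not visible and may contain a reason. A reader might infer an undocumented deviation; that cannot be shown. Permission to choose another baseline still does not make a pre-placebo value a sound reference for on-drug counts.
- **Placebo observations are not counted as on-drug events.** A reader might infer that they are. The treatment-emergent window rules this out; only the reference value is early.
- **Some tables do count from the start of drug.** For L200/I-L/I the previous-study baseline is the pre-drug value. The missing view concerns P-L/I and its contribution to the pooled columns.
- **Predose FEV1 falls do not contaminate L/I Overall.** They are shown by visit and treatment group with the baseline stated.
- **There are partial remedies.** Eye findings are listed, so a rare lens shift can be traced child by child. A 109/011B Placebo column stands beside the Study 110 columns, though not linked by subject. Serial spirometry counts same-day falls from predose on Days 1 and 15. Under efficacy, P-L/I change in ppFEV1 from the current-study baseline is summarised, but a summary of means does not give the number of children who fell.
- **Safety is descriptive**, with no testing. TEAEs, serial spirometry, and the threshold and LFT/ECG shift tables that say only baseline are unaffected.

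**Conclusion.** The point holds for P-L/I. No planned table counts their lens shifts, SpO2 shifts or between-visit predose FEV1 falls since they started LUM/IVA, although the protocol's baseline rule calls for these. For L200/I-L/I the departure is limited to their Study 110 column.

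The time shares (92% at Day 15, falling to 20% at Week 96) follow from the documents if there is no roll-over gap. The litre offset of about 0.06 to 0.09 L is for one example child and rests on assumed height and growth; it matters at early visits, since later falls include growth under either baseline. A reader might infer a particular rate of missed or false safety signals. The documents do not support one: they give no placebo-era lens or SpO2 rate and no within-child FEV1 variability.

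The continuous changes in 10.1.2.2 are a smaller matter, because raw values by visit allow the mean change since Day 1 to be approximated. Overall this should be fixed, at low cost, because it affects how the primary endpoint is read.

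**What to change.** 1. In the Study 110 columns of the SpO2 and slit-lamp shift tables, use the last value before the first Study 110 dose for both groups and Overall.
2. In L/I Overall, use the last value before the first LUM/IVA dose: the previous-study baseline for L200/I-L/I and the Study 110 baseline for P-L/I. Label it as such.
3. Add predose ppFEV1 and FEV1 fall counts and a listing flag from the Study 110 baseline on the 110 Safety Set, at least for P-L/I.
4. Keep the previous-study-baseline tables as supplementary.

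Optionally, add P-L/I tables of laboratory, ECG, vital-sign and SpO2 change from the current-study baseline, as SAP 10.1.1 already does for efficacy.

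The cost is SAP wording, a baseline flag in the programs and a few more tables. Day 1 spirometry, SpO2 and eye examinations are already scheduled or carried over from the previous study. Where the eye examination is carried over, the baseline may be up to 3 months old, and a footnote should say so.

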10.4.7 Physical Examination

Physical examination findings will be presented as a data listing for Cumulative Study Period in Treatment Cohort Period 1.

10.4.8 Spirometry

Treatment Cohort Period 1

Analysis of Predose Spirometry at Each Postdose Visit

Spirometry data will be summarized descriptively as safety-supporting data at each visit during the Cumulative Study Period by treatment group (L200/I-L/I and P-L/I) based on the Safety Set. The following summary (number and percentage of subjects) will be provided:

- Absolute change from previous study baseline in predose ppFEV₁ ≤ -5 percentage points
- Absolute change from previous study baseline in predose ppFEV₁ ≤ -10 percentage points
- Relative change from previous study baseline in predose ppFEV₁ ≤ -5 %
- Relative change from previous study baseline in predose ppFEV₁ ≤ -10 %
- Absolute change from previous study baseline in predose FEV₁ ≤ -0.05L
- Absolute change from previous study baseline in predose FEV₁ ≤ -0.10L
- Relative change from previous study baseline in predose FEV₁ ≤ -5%
- Relative change from previous study baseline in predose FEV₁ ≤ -10%

Subjects with ≥5 percentage points decrease in absolute change from previous study baseline in ppFEV₁ or ≥0.05 L decrease in absolute change from previous study baseline in FEV₁ at any visit during the Cumulative Study Period will be listed based on the Safety Set. The listing will include raw values and absolute/relative changes from previous study baseline in ppFEV₁ and FEV₁ at all visits during the Cumulative Study Period.

Analysis of Serial Spirometry

Based on the 110 Safety Set for the Current Study Period, raw values and absolute change from predose assessment in postdose ppFEV₁ and FEV₁ will be summarized by visit and by time point. The number and percentage of subjects with ≥5, ≥10, ≥15, and ≥20 percentage points decrease in the absolute change from predose to postdose in ppFEV₁ will also be summarized by visit and time point.

The summary tables will include two treatment groups (L200/I-L/I and P-L/I). For treatment L200/I-L/I, separate summaries will also be provided by previous studies (Study 109 and 011B). For both of the summaries, the mean values along with the 95% CIs based on Normal approximation will be plotted against visits and time points.

10.5 Narratives Listings

Narratives listings will be provided for subjects with any of the following events that occurred by the study cutoff date in the Cumulative Study Period of Treatment Cohort Period 1 and the study cutoff date of the Treatment Cohort Period 2 separately.

- Death
- Serious AEs
- TEAEs leading to treatment discontinuation
- Pregnancy
- LFT elevations meeting at least 1 of the following criteria:
 - ALT or AST >5xULN (regardless of total bilirubin) during the treatment-emergent period
 - ALT or AST >3xULN and total bilirubin >2xULN during the treatment-emergent period

